## **4.3 Study Enrollment Procedures**

Recruitment. Potential participants will be recruited either by self-referral (i.e., opt out letters, toll free number from advertisements) or by provider referral. To promote self-referral, informational posters, flyers, and business cards will be placed at participating sites. Veterans who are interested in participating may refer themselves by contacting VA Connecticut study staff using a toll-free number listed on the materials. For provider referral, patients will be recruited during primary care or mental health visits in the study settings. We will use the national corporate data warehouse (CDW) data obtained from the VA electronic health record (EHR) to identify eligible patients based on ICD10 musculoskeletal diagnosis code, present of at least 2 pain reports of 4 or great in the prior 12 months, absence of palliative or hospice care, and absence of dementia diagnosis. The national CDW database will be accessed by a computerized referral alert built during the UG3 period and installed at each of the recruiting sites. The alert will query the CDW data automatically. An EHR alert to the treating provider will be visible to the

treating provider during a scheduled clinic appointment. The EHR alert will contain three elements: Notification that the patient could benefit from CBT-CP, brief messages describing CBT for pain broadly (not specifying anything about either treatment under consideration, simply stating that they are eligible for CBT for chronic pain), suggestions for presenting the referral to the patient, and a hyperlink that will automatically place the inter-facility referral to VACHS study staff when clicked. We have chosen not to discuss the possibility of referral to different forms of CBT-CP because we want the trial to mimic routine care and in routine care there would not be randomization and patients may not be able to choose their specific form of treatment (e.g., in-person, telehealth, individual, group). In cases where visit time is short or if for any reason clinicians do not want to introduce the referral to COPES/CBT-CP at that visit, providers may click a link that requests they be notified again at the patient's next visit. When patients agree to be referred or to speak to study staff to learn more about CBT for chronic pain, the provider will simply click the hyperlink embedded in the alert to generate an inter-facility consult to the study staff.

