## **9.6 Data Analyses**

Quantitative Analysis. As an estimate of uptake, we will present the proportion of patients who agree to be randomized out of all who are offered referral to treatment in our study. Randomization success will be assessed by side-by-side summaries of

baseline demographic and clinical characteristics of subjects by treatment group. Analyses of all outcomes will be done according to the intent-to-treat principle.

Primary Analysis. We will test and estimate the difference between COPES and CBT-CP in terms of BPI interference by using a linear mixed-effects model which simultaneously models all available BPI interference measurements including baseline. The model will contain fixed effects for treatment (categorical: COPES vs. CBT-CP), site (categorical), gender (categorical), time (categorical: baseline, 1, 4, 6, 12 months), and the treatment-by-time interaction. The only covariates that will be included in the primary and secondary analysis (including subgroup analyses) are site and gender. We are adjusting for these 2 variables because they are used for stratification in randomization. An unstructured variance-covariance matrix will be used to model correlations among repeated measures within a subject, and a therapist random effect will be used to model the correlation of outcomes in subjects who share the same therapist. Because this is a randomized trial, in the model above we will impose the constraint that the means for the two groups are equal at baseline (that is, we will perform a constrained longitudinal data analysis). Following the CONSORT recommendations, we will not perform any test for baseline differences as these tests are not needed in a randomized clinical trial “Such significance tests assess the probability that observed baseline differences could have occurred by chance; however, we know that any differences are caused by chance” This model will allow us not only to assess the between-group difference at 4 months (primary endpoint), but also to evaluate in secondary analyses whether between-group differences are maintained over time (at 6 and 12 months). Results will be summarized as least-squares means (and their 95% confidence interval) within and between groups. The primary analysis will be conducted at significance level 0.05.

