Qualitative analysis. We will utilize data reduction strategies to sort, focus, discard and organize data to draw inferences regarding the implementation interventions in place at each facility. We will develop a template summary of data at each facility according to a small set of pre-determined domains that align with the interview guides developed for each group of respondents. Once we have developed that summary for each facility, we will create a matrix across all facilities to understand the major issues with regards to implementation. Matrices streamline the process of noting, simultaneously and systematically, the similarities, differences and trends in response across a group of informants. All interviews and focus groups will be digitally recorded for verbatim transcription (either transcribed by the transcription service previously described or through VA MS Teams software and reviewed by study staff). Analysis of qualitative data will be

conducted using ATLAS.ti, a qualitative data analysis software program allowing fluid interaction of data across types and sources.

Examination of key components of the facilitation approach. Using CFIR domains and constructs we will systematically consider strengths and weaknesses of our implementation strategy in the formative evaluation. We will collect qualitative and quantitative data prior to, during, and at completion of the COPES ExTRA study. We will use the RE-AIM framework to evaluate the summative success of the COPES and CBT-CP implementation. Reach will be evaluated by determining the refusal rate (percentage of those patients for whom an alert was triggered but the referral was not made and demographic characteristics of Veterans who participate versus those who do not). Refusal rates will be calculated overall and for each site.

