### **10.3.3 Metrics**

When patients are referred to the study, they will be assigned a sequential study ID and tracked in the study database. The database will contain the disposition of the participant at each decision point (eligible/not eligible/reason not eligible, consented/declined, randomization result, number of sessions, completion of follow-ups). We will audit the database regularly to ensure that all referred patients are accounted for and the disposition of each participant is correctly captured.

Outcome measures are collected by the IVR system, the system will not allow patients to enter answers that are outside the data range for each question. If a patient does not complete follow-up assessments, staff will follow written procedures to reduce missing data including contacting patients by phone and offering the opportunity to complete measures by IVR automated call sent at the time of the contact and a mailed survey. As with our prior studies that have used an IVR system, each morning study staff check the system for alerts (e.g., a participant connected to the Veteran Crisis line, a follow-up measure was not completed, the participant left a message for staff).

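### The Reach refusal rate counts alerted patients who were never asked, and possibly some who enrol by self-referral, as refusals; uptake is also left undefined for self-referred patients

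*Combined protocol and SAP*

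**What the plan says.** **Reach.** Section 9.6, in the paragraph on the key components of the facilitation approach, evaluates Reach by a refusal rate, given as the "percentage of those patients for whom an alert was triggered but the referral was not made", together with a demographic comparison of Veterans who do and do not take part. It adds: "Refusal rates will be calculated overall and for each site". No split by reason, or by who declined, is planned.

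**Entry to the study.** Section 4.3 gives two routes: "Potential participants will be recruited either by self-referral (i.e., opt out letters, toll free number from advertisements) or by provider referral". On the provider route, an alert appears at a clinic visit. If time is short, or "if for any reason clinicians do not want to introduce the referral to COPES/CBT-CP at that visit", then "providers may click a link that requests they be notified again at the" patient's next visit. A referral is generated by a further click: "When patients agree to be referred or to speak to study staff to learn more about CBT for chronic pain", the provider uses the link in the alert. No click or record is described for an offer that the patient declines.

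**Uptake.** The opening of section 9.6 defines uptake as "the proportion of patients who agree to be randomized out of all who are offered referral to treatment in our study". The Précis (Design and Outcomes) lists uptake among the things to be evaluated across groups where disparities are possible, such as gender and race/ethnicity.

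**Tracking.** Section 10.3.3 starts disposition tracking at referral: "When patients are referred to the study, they will be assigned a sequential study ID and tracked in the study database". Section 9.2 (Treatment Assignment Procedures) says that the source of referral, self or provider, is recorded. The only analysis planned by recruitment type (section 9.6, Recruitment Method) describes that variable and compares baseline characteristics.

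**The concern.** A refusal rate will be read as the share of patients who turned the treatment down. The rule in section 9.6 counts something wider, namely every alerted patient without a referral. Part of that group never heard of the treatment, because the provider put the alert off and never came back to it. Another part may have joined the trial by answering a letter or calling the toll-free number.

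What is at stake is a RE-AIM result that will be reported overall and for each site. Sites where providers use the alert less would show higher refusal even if patients there were just as willing. The planners of a later roll-out would then look for the obstacle among patients when it lay in the use of the alert.

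Uptake raises a lesser question of the same kind. The plan has two recruitment routes, but the uptake definition does not mention the second.

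**Working it through.** The plan states no uptake, Reach or refusal figure, so there is nothing to reproduce. The number of alerts, offers and letters and the self-referred share are not in the documents. All percentages below are assumed and only illustrate how the definitions behave.

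**1. Who counts as a refusal.** Setting the Reach rule (9.6) beside the enrolment procedure (4.3):

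| Alerted patient | Asked? | Referral made? | Counted as refusal? |
|---|---|---|---|
| Asked, agrees, referred | Yes | Yes | No |
| Asked, declines | Yes | No | Yes, correctly |
| Deferred, then referred at a later visit | Yes | Yes | Need not be |
| Deferred or ignored, never raised | No | No | Yes |
| Not referred, later enrols by letter or toll-free number | Either | No | Yes, read literally |

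The last two rows are the defect.

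**2. Effect of patients never asked.** Let f be the share of alerted patients to whom the provider never raises the referral, and r the share of those asked who decline. Assume that everyone who is asked and agrees is referred. Then

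reported refusal rate = f + (1 − f) × r.

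With r = 20%:

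- f = 0: 0 + 1 × 0.20 = 20%
- f = 20%: 0.20 + 0.80 × 0.20 = 36%
- f = 50%: 0.50 + 0.50 × 0.20 = 60%
- f = 80%: 0.80 + 0.20 × 0.20 = 84%

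With r = 50%, the same values of f give 50%, 60%, 75% and 90%. The excess over r is f × (1 − r), which is never negative. Two sites with the same r = 20% but f = 20% and f = 50% would differ by 60 − 36 = 24 percentage points through provider behaviour alone.

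**3. Effect of self-referral.** With A alerted patients, each one who enrols by self-referral without a provider referral adds 1/A to the refusal rate while also being a trial participant.

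**4. Uptake under three readings.** Let p be uptake on the provider route, q uptake among letter recipients, and s the self-referred share of those randomised, treated here as all recruited by letter. Take p = 30% and s = 50%.

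- Self-referred patients in neither numerator nor denominator: 30%, no bias.
- Self-referred patients in the numerator only: p / (1 − s) = 0.30 / 0.50 = 60%.
- Letter recipients counted as offered: 1 / [(1 − s)/p + s/q]. At q = 5% this is 1 / (1.667 + 10) = 8.6%; at q = 10%, 15%; at q = 30%, 30%; at q = 50%, 37.5%.

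The same trial could report a figure above, at or below the provider-route value, depending on a choice that the plan does not state.

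**The case against.** The best defence of the Reach measure is that section 9.6 gives its own operational definition and never calls it patient refusal. Deferral is not final, because the alert can come back at the next visit. Provider behaviour is also studied elsewhere: the RE-AIM text measures Adoption by providers' reported willingness to refer and looks at referral rates over time, and providers are interviewed. These points limit the matter but do not remove it. Patients whose deferral is never followed by a referral remain in the count. Adoption is a measure on providers and takes no unasked patient out of the refusal rate. Whatever the definition, a quantity named refusal will be read as refusal.

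A reader might go further and infer that uptake is inflated, because self-referred patients enter its numerator without being in its denominator. The documents do not support that. A proportion out of all who are offered referral ordinarily limits the numerator to those offered, the sentence does not say who makes the offer, and recipients of opt-out letters could count as offered. The numerator-only reading is one of three. Nor is it an error that uptake and Reach have different denominators: one runs from offer to randomisation, the other from alert to referral. No uptake by site is planned, so no site comparison of uptake is at risk. Finally, it cannot be said that a declined offer leaves no record. Section 10.3.3 describes the study database only, the alert is a separate system in the health record, and the documents are silent on what that system stores.

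**Conclusion.** The point holds for Reach. As defined, the refusal rate exceeds the share of asked patients who decline whenever some alerted patients are never asked and not everyone who is asked declines. Read literally, it also counts alerted patients who enrol by self-referral. The size is unknown. The illustration (36% to 84% against a true 20%) rests on assumed shares never asked of 20% to 80%.

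For uptake the finding is only that the definition is incomplete. It does not say how self-referred patients or letter recipients enter, and no source is described for the count of offers that patients decline. Neither the direction nor the size of any bias can be derived from the documents.

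Severity is minor. Both measures are descriptive, and neither the primary analysis nor any other randomised comparison depends on them.

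**What to change.** **Reach (section 9.6, facilitation paragraph).**

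- Rename the measure *alerted but not referred*.
- Count each patient once, by final alert status, so that a deferral followed by a referral is a referral.
- Do not count alerted patients who enrol by self-referral as not reached; show them on their own line.
- Where alert logs allow, split the remainder into deferred or not raised and closed without referral. Keep the word refusal for patients recorded as having been asked and having declined.

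**Uptake (opening of section 9.6).** Report uptake by recruitment route, using the source of referral that section 9.2 already records, with numerator and denominator from the same route. For the provider route, use patients offered referral if declined offers are recorded. If they are not, say so and start from patients with an alert. For the self-referral route, state the starting count, such as letters sent or calls received.

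**Cost.** A few sentences in section 9.6 and slightly more descriptive tabulation. Triggered alerts must be counted anyway for the planned measure. The finer split and the letter denominator depend on alert logs and mailing lists having been kept, which the sponsor should confirm first.

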## **9.2 Sample Size and Randomization**

Assuming a standard deviation of BPI interference of 2.4 (as observed in a previous study (SCOPE)), a total sample size of 610 subjects (305 per group) would provide 80% power to detect a mean difference in BPI interference of 0.55 between groups at 4 months using a two-sided t-test at significance level  $\alpha=0.05$ , and 90% power to detect a difference of 0.63. To account for an expected attrition rate of 20%, we will enroll a total of 764 participants (382 per group). Half of the participants will be female.

Although the randomization will be done at the patient level, there may be some clustering due to the therapist delivering the intervention. We conducted a simulation study to investigate the effect of this clustering on power. We assumed that in the COPEs arm (treatment delivered remotely by IVR) 9 therapists will be delivering the intervention (each to an equal number of subjects), and in the synchronous CBT arm 38 therapists will be delivering the intervention. Based on a prior pain trial of group cognitive behavioral treatments, we used an estimate of therapist-level intracluster correlation coefficient (ICC) of 0.01. Simulations (N=100000) showed that we will

have at least 84% power to detect a difference in BPI of 0.65 with an ICC of 0.01 or less using a mixed model on the outcome at 4 months with a therapist random effect.

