Sensitivity Analyses. If there is heterogeneity in therapist-specific time trends, then our primary analysis may have an inflated Type 1 error rate. As a first sensitivity analysis, we will use the 4-month outcome as the dependent variable in a mixed model ANCOVA. The model will have fixed effects for treatment, site, gender, baseline BPI interference, and a therapist random effect. To deal with missing data, this analysis will be applied to multiple imputed datasets (see Missing Data Sensitivity Analyses section). We will check whether the conclusion from this analysis regarding the treatment effect is consistent with the conclusion from the primary analysis.

As a second sensitivity analysis, we will use a mixed model similar to the primary analysis model, except that time will be treated as continuous. We will check the linear time assumption by considering other polynomials (e.g. quadratic, cubic).

Secondary Analyses. We will use Holm's correction to adjust for multiple secondary analyses. We will also conduct a per protocol analysis as an adjunct to the ITT primary analysis defining a "dose" of treatment as having attended/answered calls for 3 treatment sessions.

IVR-collected data. Analysis of the continuous secondary outcomes collected by IVR (PEG-3, PHQ-8, Pain Catastrophizing Scale, Insomnia Severity Index, Pain Self-Efficacy Scale,) will be similar to the primary analysis. We will use a generalized mixed model for ordinal data to analyze the Patient Global Impression of Change outcome.

We will compare treatment dose (number of sessions, a count variable) and treatment satisfaction at 4 months (continuous) between groups by using a negative binomial generalized linear mixed model and linear mixed model, respectively. The models will include treatment, site and gender as fixed effects, and a random effect for therapist.

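### The primary model's therapist random effect also covers the pre-treatment baseline, so the 4-month standard error is likely too small and the 5% test likely runs above 5%

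*Combined protocol and SAP*

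**What the plan says.** Section 9.6 (Primary Analysis) specifies a linear mixed model that "simultaneously models all available BPI interference measurements including baseline". Its within-person structure is free: "An unstructured variance-covariance matrix will be used to model correlations among repeated measures within a subject". For clustering, "a therapist random effect will be used to model the correlation of outcomes in subjects who share the same therapist"; no therapist-by-time term is listed. The model will also "impose the constraint that the means for the two groups are equal at baseline". The test is at 0.05.

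Sections 4.3, 6.2.2 (Enrollment) and 9.2 (Treatment Assignment Procedures) place randomisation after the baseline assessment. Other parts of Section 6.2.2 are less clear on the order, but the Précis and Section 3 still put baseline before treatment starts.

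In Section 9.2, "we used an estimate of therapist-level intracluster correlation coefficient (ICC) of 0.01", with 9 COPES and 38 synchronous therapists. That power simulation used a mixed model for the 4-month outcome alone.

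Section 9.6 (Sensitivity Analyses) states: "If there is heterogeneity in therapist-specific time trends, then our primary analysis may have an inflated Type 1 error rate". It plans a 4-month ANCOVA with a therapist random effect on multiply imputed data, and will check whether the two conclusions agree. The second sensitivity analysis is "a mixed model similar to the primary analysis model, except that time will be treated as continuous".

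**The concern.** A therapist's influence on a baseline score is zero, because treatment has not begun. If therapists differ in effectiveness, their effect is absent at baseline and present at 4 months. A common intercept says the opposite: that the same effect is already visible at baseline. The model then treats each therapist's mean baseline score as a measurement of that therapist's effect and adjusts for it. Most of the therapist variance is thereby removed from the fitted standard error, while all of it remains in the actual sampling variation.

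So, wherever therapist variance arises after baseline, differing therapist time trends follow from the timing of the baseline; they are not a remote contingency. The affected test decides the trial. An understated standard error raises the chance of a false difference in either direction and narrows the 4-month interval. The continuous secondary outcomes follow the same pattern and inherit the problem.

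**Working it through.** **Inputs.** From Section 9.2: SD 2.4 (variance 5.76), 305 per arm, 9 and 38 therapists, ICC 0.01. Assumed: correlation r between baseline and 4 months, complete data, equal caseloads, the same ICC in both arms, and no therapist effect at baseline.

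**The plan's own figures.** With SD 2.4 and 305 per arm, power is 80.8% for a difference of 0.55 and 90.0% for 0.63, as stated. For the clustered claim:

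- Therapist variance of the contrast = 0.0576 × (1/9 + 1/38) = 0.0079.
- Remaining variance = 0.99 × 5.76 × 2/305 = 0.0374.
- SE = √0.0453 = 0.213. Power for 0.65 is 86.3% (normal) or 84.8% (t, 45 df), against a stated minimum of 84%.

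These figures reproduce, but they describe a 4-month-only model, not the longitudinal primary model.

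**Closed form for the primary model.** Let τ = 0.0576 and s = 0.99 × 5.76/m, with m patients per therapist. With complete data, the fitted and actual variances of one therapist's baseline-adjusted 4-month mean are approximately:

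- fitted: (τ + s) − (τ + r·s)²/(τ + s)
- actual: τ + s(1 − r²)

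Divide by the number of therapists in each arm and add the arms. At r = 0.6:

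- COPES: m = 33.9, s = 0.1683; fitted 0.1146, actual 0.1653.
- Synchronous: m = 8.03, s = 0.7105; fitted 0.4632, actual 0.5123.
- Fitted SE = √(0.1146/9 + 0.4632/38) = 0.158.
- Actual SE = √(0.1653/9 + 0.5123/38) = 0.178.
- With no therapist variance at all, SE = √(0.99 × 5.76 × 0.64 × 2/305) = 0.155.

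The therapist term therefore adds little to the fitted standard error. The rejection rate is 2 × [1 − Φ(1.96 × 0.1579/0.1785)] = 8.3%.

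**Simulation.** REML fits of the constrained longitudinal model under no treatment effect, 10,000 trials per cell, ICC 0.01. Site and gender were omitted.

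| r | Patients per arm | Fitted SE | Actual SE | Rejects, normal | t, 45 df | t, 8 df |
|---|---|---|---|---|---|---|
| 0.5 | 305 | 0.172 | 0.189 | 7.7% | 6.9% | 3.8% |
| 0.6 | 305 | 0.158 | 0.178 | 8.5% | 7.7% | 4.3% |
| 0.7 | 305 | 0.141 | 0.164 | 9.7% | 8.7% | 4.9% |
| 0.5 | about 380 | 0.154 | 0.175 | 8.6% | 7.7% | 4.3% |
| 0.6 | about 380 | 0.142 | 0.165 | 9.5% | 8.6% | 4.9% |
| 0.7 | about 380 | 0.126 | 0.152 | 10.6% | 9.7% | 5.7% |

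A second simulation at 305 per arm gave 8.0% and 11.3% at r = 0.5 and 0.7. Outside that range, r = 0.3 gives 6.5–6.9% and r = 0.8 gives 11.8–12.7%. At r = 0.6 and 305 per arm, ICC 0.005 gives 6.7% and ICC 0.02 gives 12.2%.

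**Controls.** With no therapist effect, the rate is 5.1%. With a therapist effect that also exists at baseline, it is 5.2%. These isolate the cause.

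**Alternatives.** With the therapist effect on post-baseline visits only, the rate is 5.0–5.1% (4.6% in the second simulation). The plan's ANCOVA gives 5.8–6.3% with normal critical values and 5.2–5.6% with t on 45 df.

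**The case against.** The plan discloses the risk and prespecifies a sound check, so a reader who inferred a hidden error would be wrong. That stands. But disclosure does not change which model decides the trial, and no rule covers disagreement between the two.

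A reader might also infer that 8–11% follows from the plan's ICC alone. It does not:

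- The documents give neither the baseline to 4-month correlation nor the degrees-of-freedom method. With t on 8 df (9 COPES therapists minus 1) the excess disappears, although the standard error is still too small.
- The ICC comes from a trial of group treatment, and Section 9.2 allows for 0.01 or less. COPES is delivered centrally with manuals and scripts, yet its 9 therapists supply (1/9)/(1/9 + 1/38) = 81% of the therapist variance. Take a fitted SE of 0.156 at r = 0.6 and an actual variance of 0.156² + 5.76 × (ICC in COPES/9 + 0.01/38). The rate is then 8.9% at a COPES ICC of 0.01, and 7.3%, 6.5% and 5.7% at 0.005, 0.0025 and 0.
- Random allocation to therapists within arm is not described. Clustering from caseload mix is present at baseline, where a common intercept is right. If half the clustering arises after baseline, the same formula gives 6.9%.
- Participants who never meet a therapist, attrition, unequal caseloads and site effects were not simulated.

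Finally, the text does not state how the therapist term loads at baseline. A common intercept is the natural reading, and the plan's own caveat about therapist time trends makes sense only on it.

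**Conclusion.** The concern holds. As naturally read, the primary model understates the 4-month standard error whenever therapist effects emerge after baseline. At ICC 0.01 in both arms, the nominal 5% test runs at about 8–11% for correlations of 0.5–0.7 with large degrees of freedom. The wider range is about 6.5–13% for correlations of 0.3–0.8. With t on 45 df it is about 7–10% for correlations of 0.5–0.7, and with t on 8 df about 4–6%. A lower COPES ICC, or clustering already present at baseline, reduces the excess.

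The mechanism is firm; the exact size depends on quantities the plan does not give. It is also tempting to conclude that the ANCOVA should become primary. The documents do not support that as a free improvement: Section 9.3 chose the longitudinal model so that participants with only a baseline score are included, and the ANCOVA would rely on multiple imputation instead.

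**What to change.** In Section 9.6, keep the constrained longitudinal model and replace the common therapist effect with one that is zero at baseline and applies to post-baseline visits only, ideally a therapist-by-visit effect. State the degrees-of-freedom method. Use the same structure for the continuous secondary outcomes modelled like the primary one. Keep the ANCOVA as the sensitivity analysis, and say how a disagreement would be reported. The continuous-time model as written adds no therapist slope, so it should not be relied on as a check of this problem.

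The change is a few words and about one line of model code, best made before unblinding. It still includes participants with only baseline data. The price is a wider standard error at ICC 0.01: about 10% (0.189/0.172) at r = 0.5 with 305 per arm, up to about 20% (0.152/0.126) at r = 0.7 with about 380. That is the correct width.
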